9. STUDY DEVICE MATERIALS AND MANAGEMENT

9.1. Study Device

KeraStat® Cream is a non-sterile, non-implantable wound dressing intended to act as a protective covering and provide a moist environment in the management of a variety of partial thickness dermal wounds. KeraStat® Cream is provided in a screw top tube for multiple uses. Each tube contains 1 oz (29.6 mL) of KeraStat® Cream, which contains 5% keratin protein incorporated into a cream base.

9.2. Study Device Packaging and Labeling

KeraStat Cream will be provided in a multi-use (1 oz), collapsible aluminum tube. Study device supplies will be maintained at the site under controlled conditions and dispensed by qualified personnel at the study site. Study device labels will contain information to meet the applicable regulatory requirements.

9.3. Study Device Storage

The study device must be stored at room temperature (15 to 30°C [59-86°F]). Study device must be dispensed or administered according to procedures described herein. Only subjects enrolled in the study may receive the study device, in accordance with all applicable regulatory requirements. Only authorized site staff may supply or administer the study device.

9.4. Study Device Preparation

KeraStat Cream final product will be manufactured by Dexios for KeraNetics in the form of a cream and packaged in a multi-use tube as detailed in Section 9.2. T

9.5. Administration

During the SPT, the study device (KeraStat Cream) will be administered on the infrascapular region of the back to the right of the midline by qualified personnel. The region will be cleaned with alcohol wipes and allowed to air dry. Five marks will be made using a marker to identify the test sets. These marks will be at least 4 cm apart and made in a vertical line. Once the marks are made, the back will be cleaned again with alcohol wipes and allowed to air dry. All subjects

Study: KSCM-CRD-002	Effective Date:
Version: 01	17 Jul 19

will initially receive the agents in the same order, going in descending order from a subjects' head to feet: subject device, predicate devices, positive control, and negative control.

Each agent will be administered once using the UniTest® PC (Lincoln Diagnostics, Inc), according to procedures described herein. If blood is drawn, the test is repeated at an additional mark made along the vertical line. One minute after completing the pricks, absorbent tissue is applied to remove residual extract with care taken to avoid cross contamination of sites. When administration of the pricks is completed, the subject's shirt or a sheet will be used to cover the back and keep it warm. The subject will be instructed not to scratch the test area.

9.6. Study Device Accountability

The Investigator is responsible for the study device accountability and record maintenance.

9.7. Study Device Handling and Disposal

Unused supplies will be disposed of using appropriate documentation according to International Conference on Harmonization-Good Clinical Practice (ICH-GCP), local requirements, applicable Occupational Safety and Health Administration (OSHA) and Environmental Protection Agency (EPA) regulations, and applicable study-specific procedures.

10. SCREENING ASSESSMENTS

The following assessments will be used for screening purposes only and taken after informed consent is obtained.

10.1. Demographics

Basic demographic information will be collected from the subject. This information includes age, gender, and race/ethnicity.

10.2. Medical History

Each subject will provide a brief medical history (e.g. history of allergic reactions) to ensure they meet the inclusion/exclusion criteria. The Investigator will review the completed medical history form prior to enrolling the subject in the study. The Investigator may ask the subject for additional information, as necessary.

10.3. Physical Exam and Vital Signs

An abbreviated physical exam and documentation of vital signs will be conducted by the site following the site's standard policy, prior to enrolling the subject in the study. The abbreviated physical exam includes measuring a subject's height, weight, blood pressure, pulse, temperature, and respiratory rate as well as an examination of the skin prick test region of the back.

Study: KSCM-CRD-002 Version: 01	Effective Date: 17 Jul 19
--	--

11. STUDY ENDPOINTS

11.1. Positive Reactions

During all evaluations, each site will be measured for a positive reaction. A positive reaction is present when there is a measurable wheal of 3 mm or more, surrounded by a flare. In cases where the wheal diameter is non-uniform, the longest wheal diameter should be used for the evaluation of the SPT.^{6,7} Small wheals are to be confirmed by the investigator via palpation.

11.2. Adverse and Serious Adverse Events

The Investigator is responsible for the detection and documentation of events meeting the criteria and definition of a non-serious AE or SAE as provided in this protocol. During the study, as defined from the time of informed consent until completion of study-related procedures, the Investigator or site staff will be responsible for detecting and following AEs and SAEs, as detailed in this section of the protocol. Adverse events will be reported by the subject (or, when appropriate, by a caregiver, surrogate, or the subject's legally acceptable representative).

11.2.1. Definitions

11.2.1.1. Adverse Event (AE)

An adverse event (AE) is defined as any unfavorable or unintended change in body structure, body function, laboratory result (e.g., chemistry, ECG), or worsening of a pre-existing condition associated temporally with the use of the test product, whether or not considered related to the test product.

11.2.1.2. Serious Adverse Event (SAE)

A serious adverse event (SAE) is any untoward medical occurrence that occurs irrespective of study treatment assignment, if it satisfies any of these criteria: results in death; is life-threatening; requires inpatient hospitalization or prolongs existing hospitalization; results in persistent or significant disability or incapacity or substantial disruption of the ability to conduct normal life functions; or if the event results in a congenital anomaly or birth defect. All SAEs should be reported to the study sponsor within 24 hours of the investigator being aware of the event.

11.2.2. Adverse Event Reporting

Subjects will be encouraged to spontaneously report any changes in baseline health from the time the subject enters the study through study completion. Study staff also will inquire about AEs on each visit while the subject is in the research center. All AEs/SAEs will be recorded in the source document and the case report form (CRF).

11.3. Relationship to Study Device

11.3.1. Assessment of Causality

The Investigator is obligated to assess the relationship between study device and the occurrence of each AE/SAE. The Investigator will use clinical judgment to determine the relationship.

Study: KSCM-CRD-002 Version: 01	Effective Date: 17 Jul 19
--	--

Alternative causes, such as natural history of the underlying diseases, concomitant therapy, other risk factors, and the temporal relationship of the event to the study device will be considered and investigated.

The Investigator will assess causality based on the following definitions:

- **Not Related** (the AE was more likely explained by causes other than the study treatment).
- **Related** (the study treatment and AE were closely related in time and the AE may be explained by exposure to study product: e.g., known adverse effect or recurrence on re-challenge).

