6.4. Treatment Assignment

All subjects will receive all five test agents: KeraStat Cream, KeraStat Gel, Biafine, histamine, saline.

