8. TREATMENT OF SUBJECTS

8.1. Description of Subject Device

KeraStat® Cream is a non-sterile, non-implantable wound dressing intended to act as a protective covering and provide a moist environment in the management of a variety of partial thickness dermal wounds. KeraStat® Cream is provided in a screw top tube for multiple uses. Each tube contains 1 oz (29.6 mL) of KeraStat® Cream, which contains 5% keratin protein incorporated into a cream base.

The study device is described below in Table 3.

Study: KSCM-CRD-002	Effective Date:
Version: 01	17 Jul 19

Table 3: Subject Device

	Subject Device	Predicate Device	Predicate Device	Positive Control	Negative Control
Product Name	KeraStat Cream	KeraStat Gel	Biafine	Histamine	Saline
Manufacturer	KeraNetics	KeraNetics	Johnson and Johnson	HollisterStier, LLC	McKesson
Packaging	Multi-use tube	Single-use tube	Multi-use tube	Multi-use sterile amber vial with dropper	3ml Syringes
Components	5.0% keratin, purified water, glycerin, caprylic/capric triglyceride, dimethicone, mineral oil, sodium stearoyl glutamate, sodium polyacrylate/hydrogenated polydecene/trideceth-6, phenoxyethanol, ethylhexylglycerin, and sodium hydroxide	5.0% keratin; purified water, phenoxyethanol, carbomer, sodium hydroxide, and ethylhexylglycerin	Purified water, liquid paraffin, ethylene glycol monostearate, stearic acid, propylene glycol, paraffin wax, squalane, avocado oil, trolamine/sodium alginate, triethanolamine, cetyl palmitate, methylparaben (sodium salt), sorbic acid (potassium salt), propylparaben (sodium salt), and fragrance	6.0 mg/mL	0.9% NaCl
Route of Administration	Topical	Topical	Topical	Percutaneous	Percutaneous
Physical Description	White to tan cream	Hydrogel	White to tan cream	Clear liquid	Clear liquid

Study: KSCM-CRD-002 Version: 01	Effective Date: 17 Jul 19
--	--

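### Section 11.3.1 judges each adverse event against a 'study device' with no fixed meaning, so a local event at a control or predicate site can be counted as device-related

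*Combined protocol and SAP*

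**What the plan says.** Section 11.3.1 states that "The Investigator is obligated to assess the relationship between study device and the occurrence of each AE/SAE". There are two categories. An event is not related if "the AE was more likely explained by causes other than the study treatment". It is related if "the study treatment and AE were closely related in time and the AE may be explained by exposure to study product". Before choosing, the investigator is to consider "Alternative causes, such as natural history of the underlying diseases, concomitant therapy, other risk factors" and the timing of the event.

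Section 9.5 identifies the object of that judgement: "the study device (KeraStat Cream) will be administered on the infrascapular region of the back". Section 9.1, headed Study Device, also describes Cream only. Section 8.1, however, says "The study device is described below in Table 3", and Table 3 has a column for each of the five agents.

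Section 6.4 states: "All subjects will receive all five test agents: KeraStat Cream, KeraStat Gel, Biafine, histamine, saline". Section 6.1 has all five pricked in one series on the same region of the back. The AE definition in Section 11.2.1.1 covers "any unfavorable or unintended change in body structure, body function" and ties the event to a further term, 'test product'. The Safety entry in the Synopsis plans to examine the incidence and type of AEs. Section 12 adds no AE analysis.

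**The concern.** In a trial with one product per subject, loose wording about the study device or study treatment does little harm, because both point to the same thing. Here every subject receives five agents within minutes, and two of them are controls. The term in the question and the terms in the answer can then refer to different things. An event produced by histamine or Biafine can meet the definition of a related event and be filed under a heading that Section 9 uses for Cream.

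At stake is how device-related AEs are counted and described in a study labelled Clinical Safety, including the causality statement that Section 11.5.1 requires with each initial serious AE report. The open-label investigator can see which site reacted, but nothing in the plan requires that observation to be recorded with the AE or carried into the safety summary.

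**Working it through.** The plan states no figure on this point, so there is none to reproduce. The check sets the terms side by side and then illustrates how far the count can move.

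**Terms**

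- Object of the judgement (11.3.1): 'study device'. It means Cream in 9.1 and 9.5, and all five agents through 8.1 and Table 3.
- Definitions that decide it (11.3.1): 'study treatment' and 'study product', neither defined. Three places favour reading 'study treatment' as the whole prick series: Section 6.4 lists five agents under Treatment Assignment; the Time and Events Schedule puts skin prick administration under a study treatment heading; and 11.2.1.2 speaks of study treatment assignment. This is an inference, not a definition.
- AE definition (11.2.1.1): 'test product', also undefined.

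**One event, three readings.** Take itching confined to the Biafine site on the evening of Day 1.

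1. Device and treatment both mean Cream: not related.
2. Device means everything in Table 3: related.
3. Device means Cream, but the definitions are applied literally to all five agents: related, and filed under a heading that means Cream.

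The text allows each of these. None obliges the investigator to write down Biafine.

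**Recording.** Section 11.4 asks for all relevant information on an AE in the CRF, which permits the site to be entered but does not name it. The same section asks for a diagnosis in place of individual signs and symptoms, which can remove site detail. The alternative causes named in 11.3.1 do not include the other four agents, although the list is open.

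**Illustration (assumed rates, not from the documents).** Suppose Cream causes no AE, and each of the other four agents independently causes one with probability q per subject. The number of subjects is n = 20 (Section 12.2).

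- Probability that a subject has at least one such event: p = 1 − (1 − q)^4
- Expected subjects with a related event on the pooled reading: 20p
- Chance of at least one such subject: 1 − (1 − p)^20

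| q | p | Expected of 20 | Chance of at least one |
|---|---|---|---|
| 1% | 0.0394 | 0.79 | 0.55 |
| 5% | 0.1855 | 3.71 | 0.98 |
| 10% | 0.3439 | 6.88 | >0.999 |

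On the Cream-only reading the expected number is 0 in every row. The underlying data are the same and the device-related counts differ.

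**What does not move.** Sections 6.3, 11.1 and 12.1.2 take wheal size and positive reactions from each agent's own site at each reading. No causality judgement enters them.

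**The case against.** The strongest reply is that the study's question is answered elsewhere. The objective in Section 5.1 is a humoral reaction to Cream compared with predicate devices. It is addressed through wheals measured at each site and positive responses compared in 12.1.2. No AE comparison by agent is planned. This stands. A reader might infer from 11.3.1 that Cream cannot be compared with the predicates on safety at all, and the documents do not support that.

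Second, misattribution is possible but not built in. The investigator uses clinical judgement, considers alternative causes under an open list, and records all relevant information. The CRF is not among the documents, so nobody can say from them that it lacks a site field. This also stands. The narrower point remains that the protocol does not require the agent or site to be recorded.

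Third, a reader might infer that every valid subject would carry a related AE, because Section 6.1 requires the histamine wheal to exceed the saline wheal by 4 mm. That reading is strained. The wheal is intended, it is a validity condition, and it is captured as a scheduled reading. What is fair to say is that 11.2.1.1 does not settle whether such readings are also to be reported as AEs.

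Fourth, wording cannot solve systemic events. With five agents given together, a systemic reaction cannot be assigned to one of them under any definition. This is correct, and it limits the benefit of the fix to local events.

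**Conclusion.** The point holds as a minor one. Section 11.3.1 asks for a single relationship to an object the protocol uses in two senses, and decides it with terms it does not define. A local event at a histamine, saline or predicate site can therefore be classed as related to the study device, and AE results cannot be reliably split by agent.

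The size cannot be fixed from the documents, which give no AE rates. The expected counts of 0.79, 3.71 and 6.88 rest on assumed equal and independent rates for the four other agents and no AE from Cream. They show that the reading can change the count, not what the count will be. The Synopsis promises incidence and type and does not explicitly promise a table by relatedness, so the effect is on any device-related count that is reported and on individual causality statements. The primary endpoint is untouched.

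**What to change.** - In 11.3.1, use one defined term for the object of the causality assessment, state which agents it covers, and use the same term in both category definitions.
- For each AE, record the suspected agent or site (Cream, Gel, Biafine, histamine, saline, prick procedure, or not separable) and judge relatedness to that agent.
- In 11.2.1.1, state whether wheal and flare captured as scheduled test readings at the control sites are also to be reported as AEs.
- In the Synopsis Safety entry and Section 12, tabulate AEs by agent, with a separate row for events that are not separable.

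The cost is one extra CRF item and one table, with no new visits or procedures. Systemic events will mostly fall in the not-separable row, so the gain is confined to local events.

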11.4. Recording Adverse Events

When an AE occurs, it is the responsibility of the Investigator to review all documentation (e.g., medical progress notes, laboratory, and diagnostics reports) relative to the event. The Investigator will then record all relevant information regarding an AE in the CRF.

The Investigator will attempt to establish a diagnosis of the AE based on signs, symptoms, and/or other clinical information. In such cases, the diagnosis should be documented as the AE/SAE and not the individual signs/symptoms.

11.4.1. Eliciting Adverse Event Reports

At each visit, subjects will be asked about AEs by means of a non-leading question, such as “how have you been since your last visit?” or “how has the treatment been?” In this way, possibly more mild, but clinically important, side effects of the study device can be detected. SAEs will be reported promptly to KeraNetics as described in the following table once the Investigator determines that the event meets the protocol definition of a SAE.

11.4.2. Assessment of Intensity

The Investigator will make an assessment of intensity for each AE/SAE reported during the study. The assessment will be based on the Investigator’s clinical judgment. The intensity of each AE/SAE recorded in the CRF should be assigned to one of the following categories:

- **Mild:** An event that is easily tolerated by the subject, causing minimal discomfort and not interfering with everyday activities.
- **Moderate:** An event that is sufficiently discomforting to interfere with normal everyday activities.
- **Severe:** An event that prevents normal everyday activities.

An AE that is assessed as severe should not be confused with a SAE. Severity is a category utilized for rating the intensity of an event; both AEs and SAEs can be assessed as severe.

11.5. Reporting Adverse Events

An unexpected event is one that is not consistent with the subject’s past medical history and is not evident from previous clinical experience with the test product or reasonably anticipated

Study: KSCM-CRD-002 Version: 01	Effective Date: 17 Jul 19
--	--

from information known about the test product. Events that are deemed both serious and unexpected involve special handling and reporting requirements to the IRB and FDA. All SAEs will be followed until stabilization or improvement.

11.5.1. SAE Reporting Procedures

Once an Investigator becomes aware that a SAE has occurred in a study subject, she/he will report the information as thoroughly as possible with all available details of the event to KeraNetics within 24 hours. If the Investigator does not have all information regarding an SAE, he/she will not wait to receive additional information before notifying KeraNetics of the event. The information regarding the event will be updated when additional information is received. The Investigator will always provide an assessment of causality at the time of the initial event report as described in Section 11.3.1. An email is the preferred method to transmit this information regarding a SAE to the project contact for SAE receipt. In rare circumstances and in the absence of email equipment, notification by telephone is acceptable, with a copy of the event details sent by overnight mail. Initial notification via the telephone does not replace the need for the Investigator to complete the SAE report via email within 24 hours.

11.5.1.1. Regulatory Reporting Requirements for SAEs

KeraNetics has a legal responsibility to notify, as appropriate, both the local regulatory authority and other regulatory agencies about the safety of a product under clinical investigation. Prompt notification of SAEs by the Investigator to the appropriate project contact for SAE receipt is essential so that legal obligations and ethical responsibilities towards the safety of other subjects are met.

11.5.2. Reporting Safety Information to the IRB

The Investigator, or responsible person according to local requirements, will comply with the applicable local regulatory requirements related to the reporting of SAEs to the Institutional Review Board (IRB) / Institutional Ethics Committee (IEC).

11.5.3. Protocol Deviations Due to an Emergency or Adverse Event

Any subject experiencing an emergency or adverse event requiring immediate medical attention will receive appropriate medical management by medical staff at the site and at other clinical sites as indicated. These events will be reported to KeraNetics as soon as possible. If the medical management results in departure from the study protocol, the Sponsor will be responsible for granting permission for the subject to continue in the trial if the subject is able to return to study protocol adherence in a timely fashion. If the subject cannot return to the study protocol in a timely fashion, then the subject will be discontinued from the study.

11.6. Follow-up of Adverse Events

After the initial AE/SAE report, the Investigator is required to proactively follow each subject and provide further information to Sponsor on the subject's condition. All AEs and SAEs documented at a previous visit/contact and designated as ongoing, will be reviewed at subsequent visits/contacts.

Study: KSCM-CRD-002	Effective Date:
Version: 01	17 Jul 19

All AEs and SAEs will be followed until resolution, until the condition stabilizes, until the event is otherwise explained, or until the subject is lost to follow-up. Once resolved, the appropriate CRF entries will be updated.

12. STATISTICS

12.1. Description of Statistical Methods

This is an observational study only; no formal statistics will be performed.

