
Concomitant Medication Restrictions: Corticosteroids, immunosuppressive agents, radiation or chemotherapy, topical growth factors, anxiolytics, imipramine, phenothiazine, dopamine, phenergan, clonidine, montelukast, immunotherapy, UV light therapy, H-2 antagonist, cyclosporine
		

Criteria for Evaluation:
 
Skin Reaction:
 
Primary
 
 Size of wheal for the subject device and predicate device at 15 minutes post SPT administration 
Secondary
 
 Size of wheal for the subject device and predicate device at 6 hours and 1-2 days post SPT administration 
Safety Parameters:
 
 Safety of the subjects will be monitored and adverse events recorded throughout the study 		

Statistical Methods: No formal statistics will be performed to compare the subject device and predicate device. Data will be summarized for each individual subject and time point. The number of subjects that meet criteria for a positive skin reaction to KeraStat Cream and/or a positive skin reaction to the predicate device(s) will be reported.
		

Safety: All subjects who participate in the study will be included in the safety analysis. Safety will be evaluated by examining the incidence and type of adverse events from the Screening Visit through study completion.
		

Study: KSCM-CRD-002 Version: 01	Effective Date: 17 Jul 19
--	--

FIGURE 1: TIME AND EVENTS SCHEDULE

Period	Skin Prick Test	
Visits	Screening Visit / Visit 1 Day 1	Follow-Up Visit/ Visit 2 (Day 2-3)
Screening		
Informed Consent	X	
Demography	X	
Brief Medical History	X	
Inclusion/Exclusion	X	
Safety Procedures		
*Vital Signs	X	
Abbreviated Physical Examination	X	
Adverse Events	X	X
Concomitant Medications	X	X
Study Treatment/General		
Skin Prick Administration	X	
Meal	X	
Assessments		
Evaluation of Response (15 min)	X	
Evaluation of Response (6 hrs)	X	
Evaluation of Response (24-48 hrs)		X

*Vital signs include height, weight, blood pressure, pulse, temperature, and respirations per minute.

Study: KSCM-CRD-002	Effective Date:
Version: 01	17 Jul 19

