6.3. Study Endpoints

The primary objective of the study is to assess the humoral response of KeraStat Cream compared to the predicate devices utilizing the following endpoints:

- Size of wheal for the subject device and predicate devices at 15 minutes post SPT administration
- Size of wheal for the subject device and predicate devices at 6 hours and 1 – 2 days post SPT administration
- Safety of the subjects will be monitored and adverse events recorded throughout the duration of the study

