12.1.2. Responder Summary

The total number of subjects with a positive skin reaction (i.e. wheal diameter > 3mm) will be determined for the subject device and predicate device for each evaluation time point. The proportion of subjects who have a positive response to the subject device will be compared to the proportion of subjects who have a positive response to the predicate device.

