12.2. Sample Size

A total of 20 subjects were deemed sufficient to assess the potential for a humoral response to KeraStat Cream compared to the predicate devices in support of establishing substantial equivalence. The sample size for the study is not based on any statistical considerations. Approximately 22 subjects will be enrolled to assure completion of at least 20 subjects.

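### The primary endpoint, wheal size at 15 minutes, has no across-subject analysis in Section 12, and the proportions reported in its place carry no interval

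*Combined protocol and SAP*

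**What the plan says.** **Endpoint.** Under Criteria for Evaluation, the synopsis lists as primary "Size of wheal for the subject device and predicate device at 15 minutes post SPT administration", and as secondary the same measure at 6 hours and at 1–2 days. Section 6.3 repeats it as "Size of wheal for the subject device and predicate devices at 15 minutes post SPT administration", now with predicates in the plural. Section 6.1 has the investigator measure the diameter of every wheal at each reading.

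**Analysis.** Section 12.1 opens with "This is an observational study only; no formal statistics will be performed". The synopsis says the same of the device comparison, "No formal statistics will be performed to compare the subject device and predicate device", and adds "Data will be summarized for each individual subject and time point". Section 12.1.2 gives the only between-product step: "The total number of subjects with a positive skin reaction (i.e. wheal diameter > 3mm) will be determined" for the subject device and the predicate device at each reading, and the proportion positive on the subject device "will be compared to the proportion of subjects who have a positive response to the predicate device". Section 12.3 averages diameters after a triplicate re-test, but only to classify the subject against 3 mm.

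**Purpose.** Section 12.2 says 20 subjects were judged enough to assess the response to Cream against the predicates, "in support of establishing substantial equivalence", and states openly that the number has no statistical basis.

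**The concern.** Followed as written, Section 12 never produces a group-level result on the variable that the synopsis calls primary. The reader gets counts on a dichotomised version of it, set beside the counts for one predicate when the study has two (KeraStat Gel and Biafine).

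None of these proportions comes with an interval. If few or no subjects react, the report could show 0% against 0%. A reader who knows that the study serves a substantial-equivalence argument may take that as a demonstration of no difference, when 20 subjects cannot exclude a reaction rate of practical interest. Every subject also receives every product, so a direct within-subject comparison is available, and the plan does not ask for it.

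**Working it through.** **1. What each section does with wheal size**

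- Synopsis: primary at 15 minutes; summary by individual subject and time point; number of positive subjects reported.
- Section 6.3: the same measure, for both predicates.
- Section 11.1: turns a diameter into a positive reaction (at least 3 mm, with a flare).
- Section 12.1.2: counts and proportions above 3 mm; no mean, median, paired difference or interval.
- Section 12.3: the averaged diameter is used only for classification (above 3 mm).

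So the millimetre scale reaches the individual summary and the classification, but no across-subject summary and no Cream-versus-predicate comparison.

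**2. The plan's own figure.** The 20 completers cannot be reproduced or faulted: the documents give no error rate, power, effect, SD, reaction rate or margin. The step to 22 enrolled implies 1 − 20/22 = 9.1% loss. That percentage is back-calculated from the two numbers, so it is no independent check.

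**3. Precision of one proportion at n = 20 (Clopper–Pearson)**

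- 0/20: two-sided 95% upper limit 1 − 0.025^(1/20) = 16.8%; one-sided 95% upper limit 1 − 0.05^(1/20) = 13.9%.
- 1/20: 0.1% to 24.9%.
- 2/20: 1.2% to 31.7%.
- With 18 or 22 evaluable subjects, the two-sided upper limit for zero events is 18.5% or 15.4%.

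Seen the other way, the chance of at least one positive in 20 is 1 − 0.95^20 = 64% if the true rate is 5%, and 1 − 0.90^20 = 88% if it is 10%. These rates are assumed; the documents give none for the prick test.

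**4. Precision of the paired difference in proportions (Newcombe's paired interval)**

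With no positives on either product, the Wilson upper limit for 0/20 is z²/(n + z²) = 3.84/23.84 = 0.161. Both lower limits are 0 and the correlation term is set to 0, so the interval is 0 ± 0.161.

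| Result in 20 subjects | Difference | 95% interval (points) |
|---|---|---|
| No positives on either | 0 | −16.1 to +16.1 |
| 1 positive on Cream only | +5 | −11.6 to +23.6 |
| 2 positives on Cream only | +10 | −7.7 to +30.1 |

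**5. Wheal size in mm.** The documents give no SD for the paired difference. As an illustration under normal theory, the half-width is t(0.975, 19)/√20 × SD = 2.093/4.472 × SD = 0.468 × SD. Assumed SDs of 0.5, 1, 2 and 3 mm give ±0.23, ±0.47, ±0.94 and ±1.40 mm. If many differences are exactly zero, this formula is unreliable and shows only the scale.

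**The case against.** The strongest reply is that the sponsor declared a descriptive study and the plan delivers one. Section 12.1.2 yields a positive proportion per device at each reading, the synopsis promises a summary for each subject, and Section 11.1, under the heading Study Endpoints, makes positivity the clinical reading of wheal diameter. On this view the endpoint is only loosely named, and calling the 15-minute positive proportion primary would also cure the mismatch. Much of this stands. It does not supply an interval, say which predicate is meant, or bring the synopsis and Section 12 into line.

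Several stronger readings are tempting and are not supported:

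- *The plan gives no estimate and leaves the diameters unused.* It gives descriptive proportions and individual summaries. What is missing is a group result on wheal size.
- *Section 12 contradicts itself by ruling out formal statistics and then comparing proportions.* The two agree if the comparison is descriptive, which is the natural reading, though the text does not say so.
- *The proportions will be compared by an unpaired method, to establish equivalence.* Section 12.1.2 names no method and does not mention equivalence; that purpose is stated with the sample size. The difference in marginal proportions is the same point estimate in a paired table.
- *The missing ranking in Section 6.3 is a fault of consequence.* The synopsis ranks the endpoints, and nothing is tested, so no decision turns on rank.
- *Zero or one positive per product is what will happen.* This is an assumption. The patch-test result of no reactions in 50 subjects (Section 4.1) was on intact skin. At a true rate of 10%, the chance of 0 or 1 in 20 is 0.122 + 0.270 = 39%.

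It is also fair to say that if nearly all wheals are 0 mm, a mean difference in mm adds little. That is a reason to report the distribution and the paired table beside it.

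**Conclusion.** The point holds in a limited form. The primary endpoint in the synopsis has no matching across-subject analysis in Section 12, the predicate in Section 12.1.2 is not identified, and no measure of precision is planned for results intended to support substantial equivalence. The absence of a hypothesis test is not the fault, and nothing here shows that 20 subjects is the wrong number.

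The size of the gap follows from n = 20 alone. No reactions to Cream leaves rates up to 16.8% compatible with the data, and no reactions on either product leaves a paired difference of about ±16 points. These figures assume 20 evaluable subjects and independent subjects. The millimetre half-widths rest on assumed SDs and should not be used to claim that one scale is more informative than the other. The correction should be made, because it changes what a 0% against 0% result can be taken to show.

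**What to change.** In Sections 12.1 and 12.1.2:

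1. Keep the study descriptive, but say so exactly: no hypothesis tests; estimates with 95% confidence intervals.
2. At 15 minutes, report the within-subject difference in wheal diameter (0 mm when there is no wheal) for Cream minus KeraStat Gel and for Cream minus Biafine. Show the distribution, mean, median and a 95% interval that does not rely on normality, since many values may be zero.
3. For each predicate, give the paired 2×2 table of positive reactions with a 95% interval for the paired difference in proportions. Give the exact 95% interval for the Cream-positive proportion. These remain informative if every wheal is 0 mm.
4. Use one definition of positivity. The synopsis and Section 11.1 require at least 3 mm with a flare; Sections 12.1.2 and 12.3 use more than 3 mm and do not mention a flare. The sponsor must reconcile them before the tables are built.

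If the sponsor would rather make the 15-minute positive proportion primary, the synopsis and Section 6.3 should say so; items 1, 3 and 4 are still needed.

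The cost is a few sentences and a few lines of analysis, with no new data, visits or subjects. The downside is that the report will have to show wide intervals.
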